This is a Prospective Randomized Controlled trial that will be conducted at the National Cancer Institute. All patients who are eligible for the study will be included and randomized into 3 equal groups.

PATIENTS AND METHODS

After approval from the Ethics Committee at the National Cancer Institute, Cairo University, and obtaining written informed consent, eighty-one patients with thoracic segmental pain due to metastasis, unresponsive to conventional therapy and meeting the inclusion criteria will be randomly assigned to either one of the two types of treatment, PRF or TRF lesioning of the DRG or the control group. Patients will be carefully evaluated for neurologic deficits and side effects. Assessment of pain will be done at baseline then at 1, 3, 6 months after the procedure. Randomization will be done using randomized permuted block design. Randomization list will be generated through random.org online site.

INCLUSION CRITERIA:

1. A greater than 6-month history of segmental pain of thoracic vertebral body metastasis origin.

2. Unsatisfactory pain control with oral pharmacotherapy including strong opioid with VAS >5 .
3. Absence of a chronic or progressive motor deficit.
4. Absence of significant sensory deficit.
5. No indication for percutaneous or open surgical intervention.
6. Magnetic resonance imaging and Computed Tomography evidence of thoracic involvement.
7. ASA status of II to III .
8. Age \geq 18 .
9. Body mass index (BMI) :less than forty and more than twenty .
10. Informed consent

EXCLUSION CRITERIA:

1. Known sensitivity or contraindication to injected materials: local anesthetics.
2. History of psychological disorders.
3. Evidence of significant neurological deficit.
4. Inability to lie prone.
5. Local contraindication to procedure e.g. local sepsis at the site of intervention, coagulopathy.
6. Patient refusal.

Patients will be randomly assigned and divided into 3 equal comparable groups. Before the procedure, laboratory investigations, Dorsal X-ray, CT and MRI will be done. All Patients will be interviewed and examined by physicians trained in interventional pain management. Patients will be carefully assessed on physical exam for sensory, motor, or reflex deficit and

carefully documented. Patients will be informed about the technique of the blocks, and written informed consents will be obtained.

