QOL. The EORTC **QLQ-BM22** is a sub-module of the QLQ-C30 and is an internationally recognized and validated scale used to measure QOL in bone metastases patients ²³. The QLQ-BM22, includes four subscales: painful sites, pain characteristics, functional interference, and psychosocial aspects. Both questionnaires use a 4-point Likert scale ranging from 1 (not at all) to 4 (very much) to rate each item, except for the final 2 question of the QLQ-C30 pertaining to overall QOL which is scored from 1 (very poor) to 7 (excellent). Each subscale is then linearly converted to a score from 0 to 100. For the QLQ-BM22, a higher score indicates worse symptom burden for painful sites and pain characteristics, and better functioning for functional interference and psychosocial aspects. For the QLQ-30, higher scores in the emotional, physical, and QOL scales indicate greater functioning and better ²¹.

VAS, ODI, QLQ-C30 and QLQ-BM22 will be used to evaluate pain, quality of life, and performance status before the procedure and at 3 days and 1, 3, 6 months after the procedure²⁴.

In the holding area, midazolam 0.02 mg/kg IV will be given after fixation of a 20 G cannula. All RF procedures will be performed in the hospital outpatient ambulatory care setting using local anesthesia and conscious sedation as necessary, with fluoroscopic guidance to facilitate needle placement. The segmental spinal levels treated will be selected based on the patients' pain referral pattern as determined by history and physical examination findings. After sterile skin preparation, RF will be performed with the patient in the prone position with mild flexion of the spine and the fluoroscopy beam positioned in an antero-posterior (AP) direction. A 10 cm RF needle 20 G with a 10 mm active tip. The image intensifier will be rotated in a cephalo-caudad direction until the endplates of the adjacent thoracic intervertebral discs is lined up and the transverse processes became discernable from the ribs. The needle is then inserted in a slightly medial-cephalad direction under the transverse processes, and using lateral fluoroscopic imaging, incrementally walking into the thoracic intervertebral foramen . The correct position of the needle's tip should be exactly in line with the facet joint spaces on the anteroposterior projection of the image intensifier, and in the posterior part of the foramen on the lateral projection. Once correct needle position is

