confirmed by image and since neural tissue cannot be seen on plain radiographs and the DRG may vary with respect to its spatial relationship with the intervertebral foramen, so the location of the needle tip will confirmed not only by image but also by sensory stimulation at 50 Hz. The point of maximum stimulation is where sensory response in the painful dermatome can be elicited with stimuli below 0.5 V intensity and this is designated to be the location of the DRG. Slight redirection can be done to optimize the stimulation; injection of contrast reveals epidural uptake. After establishing the site for the RF, 1 ml 2% lidocaine should be injected through the needle. The needle is then connected to a RF generator (Baylis Medical com. Inc. Canada).

Group 1: Patients will receive PRF with temperature 42°C for 480 sec., 2 active cycles per second of 20 milliseconds each , with a voltage output 40 to 60-V range, impedance ranges between 150 and 400 Ohms at all levels using Fluoroscopic guidance (FG). The block will be done as that described by **Young-Chang P. et al** ⁸.

Group 2: Patients will receive TRF with temperature 80°C for 90 sec., 2 cycles, using FG . The block will be done as that described by **Ken-ichiro U** ¹⁶.

Group 3: The control group having identical needle placement and preparation without the RF lesioning (only local anesthetic).

OUTCOME AND ASSESSMENT

Primary outcome measure:

It will include:-

-VAS, ODI, QLQ-C30 and QLQ-BM22 to evaluate pain, quality of life, and performance status at 1, 3, 6 months after the procedure.

Secondary outcome measures:

It will include :-

- Neurological defects .
- Dysthesia and hypoesthesia.
- Change in physical activities, and analgesic use.
- Any other complication from either the technique as pneumothorax or local anesthetic, anesthesia dolorosa and burning pain.
- Patients' satisfaction with analgesia through a phone call a week after procedure on 5-level likert scale, (not satisfied at all, only slightly satisfied, somewhat or partly satisfied, very satisfied, perfectly satisfied)

STATISTICS

1 - Sample size estimation:

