According to studies ^(13,15,16) , to see a significant reduction in VAS defined as at least 50% reduction, ODI, QLQ-C30 and QLQ-BM22 score ($P < 0.01$) with a background standard deviation of 1.0, significance level of 0.05 and power of a test of 80%, minimum number of patients needed would be 25 per group. Because difference in VAS , ODI, QLQ-C30 and QLQ-BM22 score will be more evidenced with control group, the number needed would be much smaller , so the total number needed in the present study would be 69 patients that will be randomized into 3 equal groups. For non-parametric correction, we increased the number to 27 patients for each group.

2- Statistical analysis plan:

Data will be analyzed using SPSS version 18.0. Numerical data will be presented as mean, standard deviation or median and range as appropriate. Categorical data will be presented as numbers and proportions. Mixed models ANOVA will be used to show effect of time on pain score and also to evaluate group interaction. Non-parametric tests ; Friedman's test will be used if data did not show normal distribution. Significance level will be considered at 0.05.

REFERENCES

1. **Smith HS.** and **Barkin RL**, Painful boney metastases, American Journal of Therapeutics , 2014 ;21(2):106-130.
2. **Patrick W.**, Bone Cancer Pain: From Mechanism to Therapy, Current opinion in supportive and palliative care 2014 ; 8(2): 83–90.
4. **Bhatia A.** , Questions Regarding "Pulsed Radiofrequency for Chronic Intractable Lumbosacral Radicular Pain: A Six-Month Cohort Study", Pain Medicine 2016; 17(5):989.
6. **R. Carter W. Jones III**, Neuroinflammatory effects of Radiofrequency, European Journal of Pain 2014; 18 :149-150.
7. **Zeldin A. and Ioscovich A.**, Pulsed Radiofrequency for Metastatic Pain Treatment, Pain Physician 2008; 11:921-922 .

8. **Young-Chang P. Arai, Makoto N., Yoshihiro Y., Maki A., Miki K., Chiharu S., Akiko K., Kazuyo K., and Tatsunori I.,** Dorsal Root Ganglion Pulsed Radiofrequency for the Management of Intractable Vertebral Metastatic Pain: A Case Series, *Pain Medicine* 2015; 16:1007 – 1012.

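### The plan has no rule for deaths or missed visits over 6 months, and its Friedman fallback would drop non-completers' earlier data and would not compare the arms

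*Combined protocol and SAP*

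**What the plan says.** The statistical analysis plan (STATISTICS, item 2) states: "Mixed models ANOVA will be used to show effect of time on pain score and also to evaluate group interaction". The fallback is: "Friedman's test will be used if data did not show normal distribution". On software it says only "Data will be analyzed using SPSS version 18.0". It names no SPSS procedure, covariance structure, estimation method or analysis population.

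The primary outcome (OUTCOME AND ASSESSMENT) is "VAS, ODI, QLQ-C30 and QLQ-BM22 to evaluate pain, quality of life, and performance status at 1, 3, 6 months after the procedure". The visit schedule appears in two forms under PATIENTS AND METHODS. One is "Assessment of pain will be done at baseline then at 1, 3, 6 months after the procedure"; the other, in the paragraph on the four instruments, is "before the procedure and at 3 days and 1, 3, 6 months after the procedure".

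The sample size section (STATISTICS, item 1) starts from 25 per group, moves to 69 in total, and ends: "For non-parametric correction, we increased the number to 27 patients for each group". The eligibility lists contain no life-expectancy criterion. The only missing-data rule in the document concerns unanswered ODI items, where the denominator is reduced. Nothing covers a patient who dies, withdraws or misses a visit.

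**The concern.** Eligible patients have had pain from thoracic vertebral metastases for more than 6 months, not controlled by treatment including strong opioids. They are then followed for 6 more months with four instruments. Some deaths and missed visits have to be expected, and the plan should say what happens to those patients' data.

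Friedman's test ranks each patient's values across visits and needs a complete set. A patient with good 1- and 3-month data who dies in month 5 would contribute nothing. The early visits, when most patients can still be assessed, would lose precision because of later events.

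The fallback also answers a different question. It tests whether scores change over time within patients. It neither compares the three arms nor tests an arm-by-time interaction. If the normality check fails, the randomised comparison has no stated analysis.

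**Working it through.** **1. Does the sample size already allow for loss?** The final figure agrees with the rest of the document: 3 × 27 = 81. The starting figure of 25 cannot be reproduced, because no between-group difference is given. The interim total of 69 is 69/3 = 23 per group. The stated reason, a non-parametric correction, can by itself account for 27. With an assumed 15% inflation, 23 × 1.15 = 26.45, which rounds up to 27. With an assumed relative efficiency of 0.955, 25/0.955 = 26.2, which also rounds up to 27. Nothing needs to be attributed to attrition, and the text attributes nothing to it.

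**2. Which patients does each named analysis use?**

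| Analysis | Patients used | Compares arms? |
|---|---|---|
| Friedman's test | every visit present | no |
| Repeated-measures (split-plot) ANOVA, SPSS GLM | every visit present | yes |
| Linear mixed model by likelihood, SPSS MIXED | all with any post-baseline visit | yes |

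The first row is the stated fallback. The main analysis could be the second or the third. A complete set means four visits under one form of the schedule and five under the other, because of the 3-day assessment.

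**3. What would restricting to completers cost?** The documents give no attrition rate, so I assume a loss L by month 6 of 10%, 25% or 40%, at a constant rate and equal across arms, with no intermittent gaps.

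- Proportion still assessed at month t: (1 − L)^(t/6).
- Completers: 1 − L.
- Standard error with completers only, relative to all patients available at month t: √[(1 − L)^(t/6) / (1 − L)].

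| L by month 6 | Per arm, month 1 | Per arm, month 3 | Completers per arm | SE ratio, month 1 | SE ratio, month 3 |
|---|---|---|---|---|---|
| 10% | 27 × 0.983 = 26.5 | 27 × 0.949 = 25.6 | 24.3 | √(0.983/0.90) = 1.04 | 1.03 |
| 25% | 27 × 0.953 = 25.7 | 27 × 0.866 = 23.4 | 20.25 | √(0.953/0.75) = 1.13 | 1.07 |
| 40% | 27 × 0.918 = 24.8 | 27 × 0.775 = 20.9 | 16.2 | √(0.918/0.60) = 1.24 | 1.14 |

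Over three arms, the month-1 values collected but not used would be about 3 × (26.5 − 24.3) = 7, 3 × (25.7 − 20.25) = 16 and 3 × (24.8 − 16.2) = 26.

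**4. The same loss as power (illustration only).** A difference of 0.8 SD gives the plan's 25 per group at two-sided 0.05 and 80% power by the normal approximation. Taking that as an assumption, pairwise power is Φ(0.8 × √(n/2) − 1.96). With 27 per arm it is 0.84. At month 1 under 40% loss, it is 0.80 with all available patients (n = 24.8) and 0.62 with completers only (n = 16.2). Under 10% loss the figures are 0.83 and 0.80.

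**The case against.** The strongest reply is that the main analysis may already be sound. A reader might infer that the plan deletes every incomplete patient from it. The text does not establish that: the words fit a linear mixed model as literally as a split-plot ANOVA, and such a model keeps partial data. The pairing with Friedman's test hints at the classical form but does not prove it. This part of the objection stands, so the loss is certain only for the fallback.

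A reader might also infer that a patient who dies in month 5 leaves every comparison in the trial. That goes too far. The plan ties its ANOVA to the pain score, and names no model specifically for ODI, the QLQ scales or the secondary outcomes. It sets out no separate comparisons at 1 or 3 months either.

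A third inference is that the arms would be made to look more alike because patients in more pain leave sooner. That is possible under complete-case analysis. It depends on how dropout relates to pain and arm, on which the documents give nothing, so I put no figure on it.

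The eligibility rules also screen out some frailer patients: ASA II to III, BMI above 20, able to lie prone, no progressive motor deficit. Attrition may therefore be modest, and at 10% the month-1 penalty is only 4%. This is fair as to size. It does not supply the missing rule, and it does not make Friedman's test a comparison of arms.

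**Conclusion.** The concern holds in part.

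- **Established from the text:** there is no provision for deaths or missed visits, no attrition allowance in the 27 per group, and a fallback that needs complete data and does not compare the arms.
- **Conditional:** the same loss of early data in the main analysis, which follows only if SPSS GLM repeated measures is meant.
- **Assumed:** the size. The month-1 standard error rises by about 4%, 13% or 24% for 10%, 25% or 40% loss, given a constant rate and equal loss across arms. The true rate could lie outside this range.

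A mixed model does not remove the problem of death. It implicitly projects month-6 values for patients who have died, so a reader should not take its 6-month estimate as the mean among patients alive at 6 months. That needs a separate analysis.

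This should be changed. It does not by itself invalidate the trial.

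**What to change.** In STATISTICS, item 2:

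1. Specify a linear mixed model (SPSS MIXED, REML) with arm, visit, arm-by-visit and baseline score, and unstructured covariance. Use every available post-baseline visit of every randomised patient, and report arm differences at 1, 3 and 6 months. State whether the 3-day assessment is one of the visits.
2. Replace Friedman's test with a between-arm non-parametric comparison at each visit on all available data: Kruskal-Wallis with pairwise Mann-Whitney tests on change from baseline.
3. Report deaths and other losses by arm and visit.
4. State that the model's 6-month estimate assumes data missing at random and is not a survivors-only mean. Add an observed-case comparison among patients alive at 6 months, noting that randomisation does not protect it, and one sensitivity analysis ranking deaths as worst.

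The cost is SAP wording and slightly more analysis work in the package already named, with no new patients or data. Recruitment closed on 30 July 2018, so enlarging the sample is no longer an option, and the last 6-month visits would have fallen around the end of January 2019. The document is dated 31 March 2019. If the data had been seen before the change is made, the new analyses must be labelled post hoc and shown beside the planned ones.

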The types of measures used to assess pain relief will include single rating scales; VAS, and multiple-dimension composite measures; Oswestry Low Back Pain Disability Questionnaire (ODI), The European Organisation for Research and Treatment of Cancer (EORTC) QLQ-C30 and QLQ-BM22.

VAS; is commonly used to rate various subjective experiences a VAS is usually a horizontal line, 100 mm in length, anchored by word descriptors at each end such as "no pain" on the left and "severe pain" on the right, as illustrated in Fig. 1. The patient marks on the line three pain ratings, corresponding to current, best and worst intensity of pain experienced over the past 24 hours. The average of the 3 ratings will be used to represent the patient's level of pain over the previous 24 hours.. The VAS score is determined by measuring in millimeters from the left hand end of the line to the point that the patient marks.

[figure not shown]

Fig.(1) VAS, used in patients diary for guide in self-score pain.

The VAS has consistently demonstrated sensitivity to changes in cancer pain associated with treatment or time) and usually shows strong associations with other pain intensity ratings, it appears adequately valid and reliable as measures of pain intensity among the many different samples of persons with cancer ¹⁷.

ODI is a self-administered questionnaire divided into ten sections, each with six items designed to assess limitations of various activities of daily living. Each section is scored on a 0 to 5 scale, with 5 representing the greatest disability. The index is calculated by dividing

the summed score by the total possible score, which is then multiplied by 100 and expressed as a percentage. Thus, for every question not answered, the denominator is reduced by 5. If a patient marked more than one statement for a question, the highest scoring statement is recorded as the true indication of disability. It takes 3.5 to 5 minutes to complete the questionnaire and approximately 1 minute to score. The scores are assessed from 0% to 20% to indicate minimal disability, 20% to 40%, to indicate moderate disability, 40% to 60% to indicate severe disability, 60% to 80% to indicate crippled, and 80% to 100% to indicate bed bound or exaggerating their symptoms¹⁸. The ODI is the most commonly used disease specific patient reported outcome tool to measure functional disability related to back pain¹⁹.

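### The SAP tests the effect of time on pain without saying which model term decides effectiveness; if the qualifying VAS is also the baseline, that test can be significant with no treatment effect

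*Combined protocol and SAP*

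**What the plan says.** All references are to the combined protocol and SAP.

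- **Analysis** (STATISTICS, Statistical analysis plan): "Mixed models ANOVA will be used to show effect of time on pain score and also to evaluate group interaction". The significance level is 0.05. Friedman's test is the only non-parametric test named. No term is designated as the test of effectiveness.
- **Entry** (INCLUSION CRITERIA, item 2): "Unsatisfactory pain control with oral pharmacotherapy including strong opioid with VAS >5". Item 1 adds: "A greater than 6-month history of segmental pain of thoracic vertebral body metastasis origin".
- **Baseline** (PATIENTS AND METHODS): "Assessment of pain will be done at baseline then at 1, 3, 6 months after the procedure". Later in that section the instruments are to be applied "before the procedure and at 3 days and 1, 3, 6 months after the procedure". No screening visit, run-in or repeat qualifying reading is described. The two statements also differ on whether there is a 3-day assessment.
- **VAS score** (PATIENTS AND METHODS): current, best and worst pain are each marked. "The average of the 3 ratings will be used to represent" the patient's pain over the previous day. The plan does not say whether the entry VAS is formed in this way.
- **Primary outcome** (OUTCOME AND ASSESSMENT): four instruments "to evaluate pain, quality of life, and performance status at 1, 3, 6 months after the procedure", with no contrast between arms named.

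**The concern.** A main effect of time in this model is pooled over PRF, TRF and control. It asks whether pain changes after the procedure in everyone, not whether the arms differ. When patients are admitted because a reading is high, part of that reading is a chance upward deviation, and the next reading is lower on average even if nothing has been done. If the admitting reading also serves as the baseline level of the time factor, the time test picks up that fall.

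The same applies to a within-arm comparison of times, which is what Friedman's test provides. If the data are judged non-normal and the plan is followed as written, no between-arm test is named at all. At stake is whether a significant fall over time could be offered as evidence that radiofrequency treatment works when it need not be.

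**Working it through.** The plan gives no figure for this point, so there is none to reproduce. The check asks how often the time test rejects when nothing is true except the entry rule.

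**Inputs from the documents.** Entry at VAS above 5; 27 patients × 3 arms = 81; baseline plus follow-ups at 1, 3 and 6 months; test level 0.05. The only SD given is 1.0 (Sample size estimation), with no statement of the population it describes.

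**Assumed inputs.** A 0–10 scale; mean VAS in the source population 5 to 8; SD 1 or 2; correlation between readings on the same patient (rho) 0.5 to 0.8; the qualifying reading is the baseline.

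**Step 1: expected fall.** For a normal score truncated at 5, with a = (5 − mean)/SD:

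fall = (1 − rho) × SD × φ(a) / (1 − Φ(a))

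- Mean 5, SD 2, rho 0.5: a = 0; 0.5 × 2 × 0.399/0.500 = 0.80 points.
- Mean 6, SD 2, rho 0.7: a = −0.5; 0.3 × 2 × 0.352/0.691 = 0.31 points.
- Mean 7, SD 1, rho 0.5: a = −2; 0.5 × 1 × 0.054/0.977 = 0.03 points.

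**Step 2: rejection rate of the time test.** Mixed ANOVA, 3 × 27 patients, four times, no effect of treatment, placebo or time, 600 simulated trials per setting:

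| Source mean | SD 1, rho 0.5 | SD 1, rho 0.7 | SD 2, rho 0.5 | SD 2, rho 0.7 |
|---|---|---|---|---|
| 5 | 99.0% | 85.0% | 98.5% | 85.8% |
| 6 | 22.7% | 15.7% | 71.2% | 42.7% |
| 7 | 6.5% | 4.8% | 22.5% | 16.2% |
| 8 | 5.7% | 5.5% | 8.8% | 6.8% |

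A second simulation at SD 2 (1,500 trials per setting, scores limited to 0–10) gave 46% at mean 6 and rho 0.7. At rho 0.8 it gave 65%, 30% and 13% for means 5, 6 and 7. A source mean below the threshold gives a larger fall (mean 4, SD 2, rho 0.5: 1.14 points). It is left out of the range because it is less likely in patients with uncontrolled pain on strong opioids.

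**Step 3: Friedman's test in one arm of 27.** At mean 5 it rejects in 44% (SD 1) and 50% (SD 2) of trials at rho 0.5, and in about 28% at rho 0.7. At mean 6 the rates for the same settings run from 5% to 19%.

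**Step 4: the between-arm term.** Over all settings run with a shared reading (30, including mean 4 and rho 0.9), the group-by-time interaction rejects in 2.7% to 6.7% of trials. Simulation error is √(0.05 × 0.95/600) = 0.9 percentage points, so this is compatible with 5%. Randomised arms share the same regression to the mean.

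**Step 5: separate baseline.** With a baseline reading distinct from the qualifying one, the time test rejects in 4.8% to 5.5% of trials in the three settings run, and the mean fall is about 0.

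**The case against.** **Nothing says a time effect would be claimed as efficacy.** A reader might infer from the order of words in the SAP that time is the leading efficacy test, or that a fall over time will be reported as proof that radiofrequency works. The documents do not support this. The same sentence names the group interaction, the trial is randomised with a control arm that has the needle procedure without lesioning, and the sample size paragraph refers to differences from control. This stands. What remains is that no term is designated, and that the non-parametric fallback contains no between-arm test.

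**The shared reading is inferred from silence.** The plan does not say that the qualifying VAS is the baseline, only nothing to the contrary. The entry score may not be the three-mark average. This stands too, so the result is conditional. The required history of more than 6 months, and averaging of three marks if used at entry, would shrink the effect without removing it.

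**The effect may be negligible.** At SD 1 and a source mean of 7 or more, the time test is at its nominal level, and patients described as intractable may well average that high. The benign end of the range is real. The scale of the entry cut is also unstated: "The VAS score is determined by measuring in millimeters from the left hand end of the line". Read as 5 mm, the cut excludes almost nobody and the rate is 4.5% to 6.2%. The SD of 1.0 suggests a 0–10 scale, but the text does not settle it.

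**The fall is small against the plan's own yardstick.** The plan looks for a halving of VAS. The largest spurious fall, 0.80 points from a mean entry score of 6.6, is 12%. It could not imitate a halving; it could still make a time test significant.

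**Conclusion.** The concern holds in a limited form. The SAP tests time pooled over the three arms, does not say which term decides effectiveness, and offers only a within-patient test if normality fails. If the qualifying and baseline readings are the same, the time test rejects in about 5% to 99% of trials with no true effect. The high end (99%) belongs to mean 5 and correlation 0.5 at either SD. The spurious fall over the assumed range is at most about 0.8 points. The documents do not fix the source mean, SD or correlation, so no single rate can be attributed to this trial.

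The randomised comparison is not biased, and nothing here suggests that a between-arm result would be wrong. The defect is that the plan leaves open whether that comparison is what decides. Regression to the mean is also only one reason not to read a time effect as efficacy. Placebo response, the lidocaine given before treatment, changes in analgesic use and loss of sicker patients can all move it.

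**What to change.** Add to the Statistical analysis plan:

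1. The effect of time and any within-arm fall, including any result from Friedman's test, are descriptive and are not evidence of effectiveness.
2. Effectiveness rests on the randomised between-arm comparison: the group-by-time interaction, or the arm difference at a stated follow-up time adjusted for baseline. Name which one.
3. If data are not normal, use a between-arm rank test on change from baseline (for example Kruskal–Wallis over the three arms).

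This takes a few sentences and no new data. The downside is that a within-arm fall can no longer be claimed as efficacy. Recruitment ended on 30 July 2018, so where analysis is already done the same statement belongs in the report.

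A baseline reading separate from the qualifying one is optional. It removes regression to the mean but none of the other influences on the time effect, and it adds little once item 1 is in place. It can be used only where such readings already exist, or in a future trial.

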Comparison between Dorsal Root Ganglion Thermal Radiofrequency versus Pulsed Radiofrequency for the Management of Intractable Metastatic Pain in Thoracic Vertebral Body

Trial registration on Clinical Trial.gov: Clinical Trials

NCT03204942 on the 2nd of July 2017

Protocol date approval by National Cancer Institute (NCI)

Anaesthesia and Pain Management Department: 11 September 2016

NCI Cairo Ethics Committee approval: 14th of February 2017

Recruitment started: 30 July 2017

Recruitment Completed: 30 July 2018

Document Date (the date on which the uploaded document was most recently updated): 31 March 2019

INTRODUCTION

Metastatic disease to the bone has been a crippling devastating complication of various cancers, with unbearable pain ¹. Knowledge surrounding the pathophysiology of painful osseous metastases is rapidly changing ². Metastatic bone pain is characteristic of cancer pain and is a form of refractory cancer pain, as the pain includes not only nociceptive but also neuropathic pain that induces a peripheral and central sensitization.

The development of medication dose-limiting side effects, limits analgesic efficacy in nearly 42% of cancer pain patients ³.

In recent years the use of pulsed radiofrequency (PRF) to treat chronic pain conditions has generated intense interest in the pain community ⁴. PRF is a minimally invasive, target-selective technique that has reported benefit at reducing post-amputation stump pain, chronic radicular/ganglion pain , neuropathic pain , and arthropathic pain ^{5,6}.

In **2008**, **Zeldin** and **Ioscovich** published 3 cases of patients who suffered from uncontrolled vertebral/paravertebral metastatic pain and were successfully treated by fluoroscopically

guided selective dorsal root ganglion (DRG) PRF (PMG-230 Baylis Medical com. Inc. Canada) ⁷. They concluded that that PRF on selective DRG bilaterally under fluoroscopic guidance in patients with pain secondary to metastasis in the Thoracic vertebral body and who were unsuccessfully treated with opioids, may offer new opportunities for metastatic pain treatment and encourage future studies.

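### For non-normal data the plan names only Friedman's test, which has no arm term, so no rank-based comparison of PRF, TRF and control is pre-specified

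*Combined protocol and SAP*

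**What the plan says.** The title announces a "Comparison between Dorsal Root Ganglion Thermal Radiofrequency versus Pulsed Radiofrequency". Under Patients and Methods, patients are to be "randomly assigned to either one of the two types of treatment, PRF or TRF lesioning of the DRG or the control group", which makes three independent groups.

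The Statistical analysis plan section sets out the main analysis: "Mixed models ANOVA will be used to show effect of time on pain score and also to evaluate group interaction". For data that are not normal it says: "Non-parametric tests ; Friedman's test will be used if data did not show normal distribution". It does not say how normality will be judged. No other non-parametric method is named anywhere in the document.

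The Sample size estimation section shows that this branch was foreseen: "For non-parametric correction, we increased the number to 27 patients for each group". The primary outcome is "VAS, ODI, QLQ-C30 and QLQ-BM22 to evaluate pain, quality of life, and performance status at 1, 3, 6 months after the procedure".

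**The concern.** The trial's question is whether the arms differ. The mixed ANOVA addresses it through the group interaction. Once an outcome is declared non-normal, the only named test looks at change across visits and ignores the arm that each patient was assigned to. The randomised comparison then has no pre-specified test for that outcome, and the choice of one is left until the data are in hand.

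Change over time is a poor stand-in for a difference between arms in this trial. Patients enter with VAS above 5, so some fall from baseline could occur in every arm through regression to the mean, and the control arm also receives local anaesthetic. A significant Friedman result would be compatible with three arms that improved equally.

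**Working it through.** **1. The two jobs and the two branches**

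| Job | Normal data | Non-normal data |
|---|---|---|
| Change over time | Mixed ANOVA | Friedman's test |
| Difference between arms over time | Mixed ANOVA (group interaction) | No test named |

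**2. Why Friedman cannot fill the empty cell**

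With n patients and k visits, let R_j be the sum over patients of the within-patient rank of visit j. The statistic is

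Q = [12 / (n k (k + 1))] × Σ R_j² − 3 n (k + 1).

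Pain assessment is described as "Assessment of pain will be done at baseline then at 1, 3, 6 months after the procedure", so k = 4. With 3 × 27 = 81 patients, Q = (12 / 1620) × Σ R_j² − 1215. Arm does not appear. Moving patients between arms leaves every R_j unchanged, and so does adding a constant to all the visits of one arm. This follows from the definition and needs no simulation.

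Running Friedman separately in each arm does not help. Significance in one arm and not in another is not a test of the difference between them.

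**3. The plan's own sample size figure**

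The section gives a "background standard deviation of 1.0, significance level of 0.05 and power of a test of 80" per cent, and 25 per group, but no between-arm difference. The 25 can therefore only be back-solved. By the normal approximation, two-sided:

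δ = √(2/25) × (1.960 + 0.842) = 0.283 × 2.802 = 0.79 SD.

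The t test gives 0.81 SD. The same section also mentions P < 0.01; that level would give 0.97 SD by the normal approximation. I use 0.8 SD below as a reference effect. It is inferred, not a value the plan states.

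**4. Illustration**

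Inputs from the document: 27 per arm; baseline and three follow-up visits; level 0.05. Assumptions: normal data, equal within-patient correlation of 0.5 (range 0.3 to 0.7), no dropout, and a fall that applies to every follow-up visit, in SD units. The between-arm test is a rank ANCOVA at 1 month as an example visit: rank of the outcome on rank of baseline plus arm, F test with 2 and 81 − 4 = 77 degrees of freedom. Simulations used 1,000 to 4,000 trials per case.

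| Fall in the three arms (SD) | Pooled Friedman significant | Rank ANCOVA significant |
|---|---|---|
| 0.3 / 0.3 / 0.3 (arms do not differ) | 67-69% (50-89% over the correlation range) | near 5% |
| 0.8 / 0 / 0 (one arm differs) | 46% (35-65%) | 91-93% (87-98%) |

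Patients and Methods also lists a 3-day assessment of the four instruments. With five visits, the first row becomes about 66% and 5%, so that visit does not change the result.

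**The case against.** The strongest reply is that this is an omission and not a wrong test. The sentence opens with a plural, Friedman is a legitimate counterpart for the time effect, and nowhere does the plan say that Friedman replaces the group comparison. A sensible analyst would add a Kruskal-Wallis or similar test. All of that stands, and it limits the point. It does not close the gap, because a test that is not named is not pre-specified, and the sample was enlarged for this very branch.

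A reader might infer two stronger things. One is that the trial carries a false-positive rate of about two in three. The document does not support this: the percentages apply only if a pooled Friedman p-value were taken as evidence of efficacy, and the plan does not state that use. The other is that the trial has no between-arm analysis at all. That is also wrong, because the mixed ANOVA covers it whenever the data are judged normal. Nor is Friedman blind to treatment, since it responds to a fall in any arm; its significance simply cannot be attributed to a difference between arms.

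It may also be said that the change comes late. Recruitment ended on 30 July 2018, so the last 6-month visit fell due around the end of January 2019, before the document date of 31 March 2019. The document does not say whether results by arm were known by then.

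**Conclusion.** The gap is real but conditional. For any outcome judged non-normal, the plan names a test of change over time and none of PRF against TRF against control. This follows from the text and from the definition of Friedman's test and rests on no assumed figure. The illustration (about 67-69% against near 5% for an equal 0.3 SD fall) shows why the one test cannot stand in for the other. It rests on the assumed correlation, normal data and no dropout, and it is not an error rate of this plan. The point should be fixed; it does not undermine the main mixed ANOVA.

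**What to change.** Replace the Friedman sentence with:

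> If an outcome is not normally distributed, the three arms will be compared at each of 1, 3 and 6 months by a rank-based test adjusted for baseline (rank of the outcome at that visit, with baseline rank as covariate). Pairwise comparisons (PRF v TRF, PRF v control, TRF v control) at a visit will be made by the same method, re-ranked within the pair, only if the three-arm test at that visit is significant at 0.05. Friedman's test will be used only to describe change over time within each arm.

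Kruskal-Wallis on change from baseline is a simpler alternative for the three-arm test. The wording keeps the plan's own trigger, so the sponsor should also state how normality is to be judged.

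The cost is three sentences, with no new data or patients. With three arms, testing pairs only after a significant overall test controls the error rate across the pairs at that visit. It lowers per-pair power slightly, from about 88% to about 86% for a 0.8 SD fall against control at 27 per arm under the assumptions above; a Holm adjustment would lower it to about 80%. Visit-by-visit tests do not give a single arm-by-time test, but they do compare the arms at every visit listed for the primary outcome. Multiplicity across visits and across the four primary instruments is a separate point. If results by arm were already known at the document date, label the change post hoc.
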